- 18b. Patients with uncontrolled diabetes having an HbA1c test result $\geq 8\%$ at the Visit 1 laboratory test.
- 19b. Patients who have a clinically significant laboratory abnormality at the Visit 1 laboratory test including (but not limited to):
- Total white blood cell count < 2500 cells/ μ L
 - AST or ALT > 2.0 X ULN or total bilirubin > 1.3 X ULN
 - Estimated Glomerular Filtration Rate (eGFR) by the Modification of Diet in Renal Disease (MDRD) equation or Bedside Schwartz equation < 55 mL/minute/1.73 m²
- 20b. Patients who in the judgment of the investigator have a clinically significant condition such as (but not limited to) unstable ischemic heart disease, New York Heart Association (NYHA) Class III/IV left ventricular failure, arrhythmia, uncontrolled hypertension, cerebrovascular disease, neurodegenerative diseases, or other neurological disease, uncontrolled hypo- and hyperthyroidism and other autoimmune diseases, hypokalemia, hyperadrenergic state, or ophthalmologic disorder or patients with a medical condition that might compromise patient safety or compliance, interfere with evaluation, or preclude completion of the study.
- 21b. Patients with a history of myocardial infarction 12 months of Visit 1.

- 22b. Patients with serious co-morbidities including, but not limited to, neurodegenerative diseases, rheumatoid arthritis and other autoimmune diseases.
- 23b. Patients with a history of alcohol or drug abuse within 12 months prior to Visit 1.
- 24b. Patients with a weight <30 kg.
- 25b. Patients aged 12 to <18 years below the 3rd percentile for weight by age (based on local growth charts or the United States Center for Disease Control growth charts, if local growth charts are not available) ([Center for Disease Control and Prevention 2000](#)).
- 26b. Patients receiving any medications in the classes listed in [Table 5-4](#) must be excluded unless they meet the criteria as specified in [Table 5-4](#).
- 27b. Patients receiving medications in the classes listed in [Table 5-2](#) must be excluded unless the medication has been stabilized for the specified period and the stated conditions have been met.
- 28b. Patients who started immunotherapy or desensitization for allergies, within 3 months prior to Visit 1, or where the maintenance dose is expected to change during the study.
- 29b. Inability to comply with all study requirements.

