2.8.3.3 Notable values

For selected laboratory parameters, abnormalities occurring at any time-point over the treatment period, considering all post-baseline on-treatment data from scheduled, unscheduled and premature discontinuation visits will be summarized.

Patients with any newly occurring or worsening on-treatment value meeting the clinically notable criteria will be counted under the applicable criteria. For a patient to meet the criterion of a newly occurring clinically notable value, the patient needs to have a baseline value which is not clinically notable for that parameter. For a patient to meet the criterion of a worsening clinically notable value, the patient needs to have a baseline value which is clinically notable and also have a worse post-baseline value. For patients with missing value in baseline, any post-baseline notable value will be considered as newly occurring.

Guidelines for clinically notable criteria for laboratory tests are based on the FDA Guidelines for adults in SI units. The criteria for clinically notable values are presented in [Table 2-3](#).

Laboratory test units will be converted to standard units. Based on agreement within our standards, if we have a multi-region study the Blood Urea Nitrogen (BUN) / Urea test would be represented as BUN [mg/dL] for the regions used to conventional results (US, Latin America) and as Urea [mmol/L] for the regions used to SI results. Therefore both BUN and Urea parameters will be included in the listings.

BUN is always reported as mg/dL and Urea as mmol/L. BUN and Urea are the same measurement in the lab and should be considered the same test. Hence for the summary tables, it is expressed in SI units. Conversion to SI units includes the factor which incorporates a conversion from BUN to Urea as well as a conversion from mg/dL to mmol/L. This is necessary because BUN is Urea Nitrogen, not Urea and there are two nitrogens in each urea molecule. The factor of 0.357 converts BUN in mg/dL to Urea in mmol/L.

Listings of patients with notable laboratory values will be provided by laboratory parameter, treatment group, and patient number.

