For summary tables and figures on laboratory parameters considering values, which are lower or greater than the limit of quantification, the following approach will be taken. For values which are flagged as lower than the lower limit of quantification, the values presented in summary tables should be multiplied by 0.5 and for values which are flagged as greater than upper limit of quantification as 1.5, the values presented in summary tables should be multiplied by 1.5. If either albumin or protein or creatinine is below the limit of quantification then the raw values would be imputed and ratios will be computed.

Additionally, box plot over time for Albumin: Creatinine ratio (ACR), Protein: Creatinine ratio (PCR) will be presented. Box plot of creatinine change from baseline values for the post-baseline visits will also be presented. Albumin: Creatinine ratio (ACR) value will be considered

missing if either the albumin or the creatinine values are missing. Similarly, Protein: Creatinine ratio (PCR) will be considered missing if either the protein or the creatinine values are missing. Mean change from baseline in creatinine will be plotted for the post-baseline visits.

Table 2-2 Direction of interest for worst case value for laboratory parameters

Laboratory parameter	Direction of interest for worst case value
A. Hematology	
Basophils	High
Eosinophils	High
Hematocrit	Low
Hemoglobin	Low
Lymphocytes	Low and high
Monocytes	High
Neutrophils	Low and high
Platelets	Low and high
RBC	Low
WBC total	Low and high
B. Chemistry	
Albumin	Low
Sodium	Low and High
Alkaline Phosphatase	High
ALT/SGPT	High
AST/SGOT	High
Bilirubin Total	High
Blood Urea Nitrogen (BUN)	High
CPK	High
Creatinine	High
Gamma GT	High
Glucose	Low and high
Potassium	Low and high
Uric acid	High

Table 2-3 Clinical notable criteria for selected laboratory tests

Laboratory parameter (unit)	Bound for notably low values	Bound for notably high values
Hematology		
Hematocrit (v/v)		
Male 12-17	0.34	
Male 18-65	0.37	
Male >=66	0.34	
Female 12-65	0.32	
Female >=66	0.31	
Hemoglobin (g/L)		
Male 12-17	100	

Laboratory parameter (unit)	Bound for notably low values	Bound for notably high values
Male >=18	110	
Female	95	
Thrombocytes (x10E ⁹ /L)	75	700
WBC's (x10 ⁹ /L)	2.8	16.0
Chemistry		
Alkaline Phosphatase (IU/L)	-	3xULN
Total Bilirubin (µmol/L)	-	34.2
Creatinine (µmol/L)		176.8
Potassium (mmol/L)	3	6
Glucose (mmol/L)	2.78	9.99
ALT/SGPT (U/L)	-	3 x ULN
AST/SGOT (U/L)	-	3 x ULN
BUN/ Urea (mmol/L)		9.99

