Sodium (mmol/L)	125	160
Gamma GT (U/L)		3 x ULN
CPK (IU/L)		4 x ULN
Urinalysis		
Dipstick blood		≥ 2+
Dipstick glucose		≥ 2+
Dipstick leukocytes		≥ 2+
Dipstick protein		≥ 2+
v = volume, ULN = upper limit of normal		

Liver function tests

To evaluate potential drug-induced liver injury, newly occurring or worsening abnormalities in liver function tests will be evaluated (see Table 2-4 for a summary of the notable values).

When a criterion contains multiple laboratory parameters, the criterion will only be considered to be met when all conditions occur at the same time (i.e., in the same sample). A case where all criteria are met at a post-baseline time point but not met at baseline will be considered as newly occurring. A case will be considered as worsening if all the criteria are met at baseline and at least one component is worsening from baseline, irrespective of whether the other(s) are better.

The number and percentage of patients with newly occurring liver enzyme abnormalities any time post-baseline will be summarized by source of patients. Listings of patients with notable liver function test lab values and liver events will be provided.

To evaluate drug induced serious hepatotoxicity eDish plots will be presented by source of patients and treatment in prior study for rollover for rollover patients. The eDish plot will reflect the worst value of each of the parameters; they do not need to occur at the same visit.

Table 2-4 Notable liver function test values

Criterion
ALT > 3 x ULN ALT > 5 x ULN ALT > 8 x ULN ALT > 10 x ULN ALT > 20 x ULN
ALT or AST > 3 x ULN ALT or AST > 5 x ULN ALT or AST > 8 x ULN ALT or AST > 10 x ULN ALT or AST > 20 x ULN
Total Bilirubin > 1 x ULN Total Bilirubin > 1.5 x ULN Total Bilirubin > 2 x ULN Total Bilirubin > 3 x ULN
ALP > 1.5 x ULN ALP > 2 x ULN ALP > 3 x ULN ALP > 5 x ULN
ALT or AST > 3 x ULN and Total Bilirubin > 1.5 x ULN ALT or AST > 3 x ULN and Total Bilirubin > 2 x ULN ALT or AST > 5 x ULN and Total Bilirubin > 2 x ULN ALT or AST > 8 x ULN and Total Bilirubin > 2 x ULN ALT or AST > 10 x ULN and Total Bilirubin > 2 x ULN ALT or AST > 20 x ULN and Total Bilirubin > 2 x ULN
ALP > 3 x ULN and Total Bilirubin > 2 x ULN ALP > 5 x ULN and Total Bilirubin > 2 x ULN
ALT or AST > 3 x ULN and Total Bilirubin > 2 x ULN and ALP ≤ 2 x ULN (Hy's law)
ALT or AST > 3 x ULN and (nausea or vomiting or fatigue or general malaise or abdominal pain or (rash and eosinophilia))*

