2.8.4.2 Vital signs

Vital signs measurements include systolic and diastolic blood pressure (SBP and DBP), pulse rate, height and body weight. Vital signs data taken on or after first intake of study drug and until 7 days after last intake of study drug are regarded as on-treatment data. Vital signs data measured more than 7 days after last intake of study drug are regarded as post-treatment data and will not be summarized. All data will be included in the analyses regardless of rescue medication use. For rollover patients, the last pre-treatment assessment in the current study (A2315 baseline) will be used in summary tables and figures. Prior study baseline will be considered as a supplementary baseline value presented in figures as well.

The following analyses will be performed by treatment group:

- absolute on-treatment values and change from baseline summarized by parameter, and visit
- the number and percentage of patients with newly occurring or worsening notable vital signs on-treatment values (see [Table 2-6](#) for definition of notable values) summarized by parameter (except height), at any time on-treatment considering all post-baseline data from scheduled, unscheduled and premature discontinuation visits.
- Vital signs will also be summarized by clinically relevant categories:
 1. Pulse rate: < 40 bpm, 40 – 90 bpm, and > 90 bpm
 2. Systolic blood pressure: < 90 mm Hg, 90 – 140 mm Hg, and > 140 mm Hg
 3. Diastolic blood pressure: < 50 mm Hg, 50 – 90 mm Hg, and > 90 mm Hg.

The same approach as for notable laboratory values will be used to define a newly occurring notable vital sign value and a worsening notable vital sign value.

Table 2-6 Clinical notable criteria for vital signs

Vital sign parameter (unit)	Lower bound of clinically notable range	Upper bound of clinically notable range
Notable value considering newly occurring or worsening cases		
Systolic blood pressure (mmHg)	< 75	> 200
Diastolic blood pressure (mmHg)	< 40	> 115
Pulse rate (bpm)	< 40	> 130
Notable change from baseline		
Systolic blood pressure (mmHg)	≤ 90 and decrease from baseline by ≥ 20	≥ 180 and increase from baseline by ≥ 20
Diastolic blood pressure (mmHg)	≤ 50 and decrease from baseline by ≥ 15	≥ 105 and increase from baseline by ≥ 15
Pulse rate (bpm)	≤ 50 and decrease from baseline by ≥ 15	≥ 120 and increase from baseline by ≥ 15
Weight (kg)	Decrease ≥ 7% from baseline	Increase ≥ 7% from baseline

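### SAP 2.8.3.3 defines a newly occurring notable value by parameter, not by direction, so a laboratory value that crosses from one notable bound to the other cannot count as new

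*SAP*

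**What the plan says.** SAP 2.8.3.3 sets out one combined count: "Patients with any newly occurring or worsening on-treatment value meeting the clinically notable criteria will be counted under the applicable criteria". It then defines the two ways into that count.

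- Newly occurring: "the patient needs to have a baseline value which is not clinically notable for that parameter".
- Worsening: "the patient needs to have a baseline value which is clinically notable and also have a worse post-baseline value".

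If the baseline is missing, any notable value after baseline is treated as newly occurring.

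Table 2-3 supplies the bounds. Five laboratory parameters have two: thrombocytes (75 and 700), WBC (2.8 and 16.0), potassium ("Potassium (mmol/L) 3 6"), glucose ("Glucose (mmol/L) 2.78 9.99") and sodium ("Sodium (mmol/L) 125 160"). The other blood tests in the table have one bound only.

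The liver-test rule later in the same section works differently. It asks whether a given criterion is met after baseline and was not met at baseline.

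SAP 2.8.4.2 carries the laboratory approach over to vital signs: "The same approach as for notable laboratory values will be used to define a newly occurring notable vital sign value".

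**The concern.** For a parameter with two bounds, notably high and notably low are different abnormalities. Someone with high glucose at baseline and low glucose on treatment has developed a new one. The newly occurring definition does not recognise this, because the baseline was already notable for glucose.

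Whether the worsening definition picks the patient up depends on what a worse value means when there are two bounds, and the SAP does not say. Two programmers following the text could produce different notable-low or notable-high counts from the same data. The trial's purpose is safety, so a count of new laboratory abnormalities by arm should not depend on an undefined word.

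One display that would have helped is gone. Protocol 9.5.2 planned laboratory shift tables against the normal range, with a group for patients who were both low and high. SAP section 4 drops them.

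**Working it through.** The plan states no figure here, so there is none to reproduce. The check applies the written rule to every transition that ends in a notable value and compares it with a rule applied to each bound.

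**Inputs.** The two definitions in SAP 2.8.3.3 and the five pairs of bounds in Table 2-3.

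**Rules.** Let L, N and H mean below the low bound, between the bounds, and above the high bound.

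- New, as written: on-treatment state is L or H, and baseline is N.
- New, by bound: on-treatment state is L or H, and baseline is not in that same state.
- Worsening, narrow reading: baseline and on-treatment state are the same, and the later value is more extreme.
- Worsening, wide reading: as the narrow reading, or the value has crossed to the opposite notable range.

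**Result.** It is the same for all five parameters. The same-direction rows assume that the later value is the more extreme one.

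| Baseline → on treatment | New, as written | New, by bound | Worsening, narrow | Worsening, wide |
|---|---|---|---|---|
| N → L or N → H | yes | yes | no | no |
| L → L or H → H | no | no | yes | yes |
| H → L | no | yes | no | yes |
| L → H | no | yes | no | yes |

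**Illustrative H → L values.** Baseline is set 10% above the high bound, and the on-treatment value 15% below the low bound.

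- Glucose: 9.99 × 1.10 = 10.99, then 2.78 × 0.85 = 2.36.
- WBC: 16.0 × 1.10 = 17.6, then 2.8 × 0.85 = 2.38.
- Potassium: 6 × 1.10 = 6.6, then 3 × 0.85 = 2.55.
- Sodium: 160 × 1.10 = 176, then 125 × 0.85 = 106.25.
- Thrombocytes: 700 × 1.10 = 770, then 75 × 0.85 = 63.75.

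None of the five is newly occurring as written; all five are when judged by bound. Only the crossing rows change between the two rules.

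**Vital signs.** The second block of Table 2-6 is directional. Take each crossing between the notable bounds of the first block:

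- Systolic pressure from above 200 to below 75 is a fall of more than 125. The block needs 90 or less with a fall of at least 20.
- Diastolic pressure from above 115 to below 40 is a fall of more than 75. The block needs 50 or less with a fall of at least 15.
- Pulse from above 130 to below 40 is a fall of more than 90. The block needs 50 or less with a fall of at least 15.

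The reverse crossings meet the mirror-image high rules: 180, 105 and 120 or more, with rises of at least 20, 15 and 15. Every vital-sign crossing is therefore already flagged.

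**The case against.** The strongest reply is that nobody need be lost. New and worsening cases enter one count, the SAP does not confine a worse value to the baseline direction, and counting under the applicable criteria fits placing a new low under the low criterion. This stands as far as it goes: a reader might infer that these patients drop out of the table, and the text supports that only on the narrow reading. It does not rescue the definition. On the wide reading the patient is recorded as worsening from a state that was absent at baseline, and the choice between readings is left to the programmer.

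Laboratory crossings also stay visible elsewhere. Worst-case values and changes from baseline are summarised, Table 2-2 takes both directions for all five parameters, and patients with notable values are listed. That is correct and limits the harm, but none of these displays counts, by arm, new lows among patients who were high at baseline.

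A reader might also infer that the rule could hide a drug-related cytopenia. The documents do not support this. Protocol 7.5 finds potential idiosyncratic reactions by a search on standardised MedDRA queries, with regular review by the data monitoring committee, and SAP 2.8.1 retrieves adverse events of special interest separately. Neither route uses the Table 2-3 classification.

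**Conclusion.** The point holds as a minor defect of definition. For five laboratory parameters, a value that crosses from one notable range to the other cannot be newly occurring, and whether it is counted at all depends on an undefined term. No primary or secondary endpoint is affected.

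The size cannot be derived, because neither document says how many patients are notable at baseline. A reader might put a percentage on the loss. With an assumed share p of patients notably high in glucose at baseline, and an assumed relative risk r of a notable low among them, the share of notable-low patients dropped is p·r / (p·r + 1 − p). With p from 2% to 5%:

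- r = 1 gives 2% to 5%.
- r = 10 gives 0.20/1.18 = 17% to 0.50/1.45 = 34%.

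Both p and r are assumptions, nothing in the documents supports a tenfold risk, and the formula applies only if every crossing is dropped. These figures should not be read as an estimate. The entry criteria point towards small numbers for glucose: Protocol 4.2 excludes new patients described as "Patients with uncontrolled diabetes having an HbA1c test result" of 8% or more. The amendment rationale says rollover patients had met this criterion in their previous study, although that was at an earlier time than the A2315 baseline.

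**What to change.** In SAP 2.8.3.3, apply both definitions to each bound, as the liver-test rule already does for each criterion:

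- Newly occurring low: on-treatment value below the low bound, baseline not below it.
- Newly occurring high: on-treatment value above the high bound, baseline not above it.
- Worsening: baseline beyond the same bound, and the post-baseline value more extreme in that direction.

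The existing handling of a missing baseline can stay. The same wording may be carried into 2.8.4.2 for consistency, but it would add no vital-sign crossing that Table 2-6 does not already flag. The cost is one sentence and minor reprogramming by bound instead of by parameter. No new data are needed.

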LIVER EVENTS	
 • ALT or $\text{AST} > 5 \times \text{ULN}$ • $\text{ALP} > 2 \times \text{ULN}$ (in the absence of known bone pathology) • $\text{TBL} > 2 \times \text{ULN}$ (in the absence of known Gilbert syndrome) • ALT or $\text{AST} > 3 \times \text{ULN}$ and $\text{INR} > 1.5$ • Potential Hy's Law cases (defined as ALT or $\text{AST} > 3 \times \text{ULN}$ and $\text{TBL} > 2 \times \text{ULN}$ [mainly conjugated fraction] without notable increase in ALP to $> 2 \times \text{ULN}$) • Any clinical event of jaundice (or equivalent term) • ALT or $\text{AST} > 3 \times \text{ULN}$ accompanied by (general) malaise, fatigue, abdominal pain, nausea, or vomiting, or rash with eosinophilia • Any adverse event potentially indicative of a liver toxicity*

*These events cover the following: hepatic failure, fibrosis and cirrhosis, and other liver damage-related conditions; the non-infectious hepatitis; the benign, malignant and unspecified liver neoplasms
TBL: total bilirubin; ULN: upper limit of normal

Table 14-2 Follow Up Requirements for Liver Events and Laboratory Triggers

Criteria	Actions required	Follow-up monitoring
Potential Hy's Law case ^a	
 • Discontinue the study treatment immediately • Hospitalize, if clinically appropriate • Establish causality • Complete liver CRF 	ALT, AST, TBL, Alb, PT/INR, ALP and γGT until resolution ^c (frequency at investigator discretion)
ALT or AST		
$> 8 \times \text{ULN}$	
 • Discontinue the study treatment immediately • Hospitalize if clinically appropriate • Establish causality • Complete liver CRF 	ALT, AST, TBL, Alb, PT/INR, ALP and γGT until resolution ^c (frequency at investigator discretion)
$> 3 \times \text{ULN}$ and $\text{INR} > 1.5$	
 • Discontinue the study treatment immediately • Hospitalize, if clinically appropriate • Establish causality • Complete liver CRF 	ALT, AST, TBL, Alb, PT/INR, ALP and γGT until resolution ^c (frequency at investigator discretion)
> 5 to $\leq 8 \times \text{ULN}$	
 • Repeat LFT within 48 hours • If elevation persists, continue follow-up monitoring • If elevation persists for more than 2 weeks, discontinue the study drug • Establish causality • Complete liver CRF 	ALT, AST, TBL, Alb, PT/INR, ALP and γGT until resolution ^c (frequency at investigator discretion)

Criteria	Actions required	Follow-up monitoring

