2.1.1.3 Baseline definition

Baseline age will be defined as the age of the patient at study entry in Study A2315 for all patients. Baseline values of other variables are defined as follows for rollover patients and new patients, respectively.

Rollover patients: For laboratory, vital signs, and ECG variables, the last pre-treatment assessment in current study (A2315 baseline) will be used as a primary baseline value for safety monitoring purpose, and prior study baseline (i.e., the baseline value from the previous QAW039 Phase 3 study) will be used as a supplementary baseline value. For other variables, prior study baseline will be used.

New patients: the last pre-treatment assessment in the current study will be used as the baseline value.

Post-baseline measurements are defined as those assessments on or after the start of study treatment in Study A2315.

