2.8.3 Laboratory data

Laboratory data consist of hematology, biochemistry and urinalysis. On-treatment laboratory data will be summarized. Laboratory data measured on or after first intake of study drug and until 7 days after last intake of study drug are regarded as on-treatment data. All data will be included in the analyses regardless of rescue medication use. The following sub-sections will describe the method of summary. For rollover patients, the last pre-treatment assessment in the current study (A2315 baseline) will be used in summary tables and figures. Prior study baseline will be considered as a supplementary baseline value presented in figures as well.

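### The Table 2-4 count of Hy's law and the other combined laboratory criteria can omit patients whose bilirubin rises after ALT/AST has fallen, or more than 7 days after the last dose, and its data window is not settled

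*SAP*

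**What the plan says.** **Same-sample rule.** In SAP 2.8.3.3, under liver function tests, a Table 2-4 criterion with more than one laboratory parameter is handled as follows: "the criterion will only be considered to be met when all conditions occur at the same time (i.e., in the same sample". This covers the ALT/AST with bilirubin rows, the ALP with bilirubin rows and the Hy's law row.

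**Data window.** SAP 2.8.3 opens with "On-treatment laboratory data will be summarized" and fixes the end of that period: values "until 7 days after last intake of study drug are regarded as on-treatment data". The general part of 2.8.3.3 says the same for notable values, "considering all post-baseline on-treatment data from scheduled, unscheduled and premature discontinuation visits will be summarized".

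**A different window in the liver paragraph.** There the SAP says that "newly occurring liver enzyme abnormalities any time post-baseline will be summarized by source of patients". SAP 2.1.1.3 gives that term no upper limit: "Post-baseline measurements are defined as those assessments on or after the start of study treatment in Study A2315".

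**eDISH.** The plot is not bound by the same-sample rule: "The eDish plot will reflect the worst value of each of the parameters; they do not need to occur at the same visit". No data cut-off is stated for it.

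**Protocol.** Appendix 2 (Table 14-1 and the footnote to Table 14-2) defines a potential Hy's law case by ALT/AST above 3 × ULN and total bilirubin above 2 × ULN without a notable ALP rise. Table 14-1 adds that the bilirubin should be mainly conjugated. Neither place sets a same-sample or time condition. At ALT/AST above 8 × ULN, Table 14-2 instructs sites to "Discontinue the study treatment immediately" and then to repeat liver tests until resolution.

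**The concern.** The protocol generates liver tests after the drug is stopped, while the analysis rules tend to remove those tests from the count they would inform. A patient who stops at ALT above 8 × ULN with normal bilirubin is followed to resolution. If bilirubin then passes 2 × ULN, the Hy's law row increments only if ALT/AST is still above 3 × ULN in that same sample and, on the natural reading, only if the sample falls within 7 days of the last dose.

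This matters because the SAP presents these analyses as its evaluation of potential drug-induced liver injury. Protocol Appendix 3 also places liver reactions on the list of potential idiosyncratic reactions, and Protocol 3.6 links that concern to the acyl glucuronide metabolite. A combined-criterion count in a safety study of this size is likely to be zero or very small, so one omitted patient can change how the row is read.

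The window is itself unsettled. Two programmers following different sentences of the SAP could obtain different Hy's law counts from the same data.

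**Working it through.** The plan gives no figure for this point, so there is none to reproduce. The check is to follow illustrative patients through the rules.

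**Inputs from the documents**
- Hy's law row (SAP Table 2-4): ALT or AST > 3 × ULN, bilirubin > 2 × ULN and ALP ≤ 2 × ULN, all in one sample.
- eDISH: highest value of each parameter, from any visit.
- Windows: last dose + 7 days (SAP 2.8.3); last dose + 30 days (the SAP's window for serious AEs, 2.5.1); no limit (SAP 2.1.1.3).

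**Illustrative patients.** These values are assumptions, not from the documents. ALP is 1 × ULN throughout. Samples are shown as day after last dose: ALT / bilirubin, in × ULN.

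| Patient | Samples | Hy's law row, to day 7 | Hy's law row, to day 30 | Hy's law row, no limit | eDISH, to day 7 | eDISH, to day 30 or no limit |
|---|---|---|---|---|---|---|
| A | 0: 9/1.0; 5: 6/2.4 | counted | counted | counted | shown | shown |
| B | 0: 9/1.0; 7: 8/1.6; 14: 5/2.6 | missed | counted | counted | not shown | shown |
| C | 0: 9/1.0; 7: 5/1.6; 14: 2.5/2.6 | missed | missed | missed | not shown | shown |
| D | 0: 9/1.0; 6: 2.5/2.6 | missed | missed | missed | shown | shown |

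Here, shown means in the quadrant with ALT > 3 and bilirubin > 2 × ULN.

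**Reading the table**
- With a 7-day limit the Hy's law row counts 1 of 4 and eDISH shows 2 of 4.
- Widening the window to 30 days rescues B only (2 of 4). C and D are held out by the same-sample rule, whatever the window.
- B and C would still enter Table 2-4's lowest combined row (ALT/AST > 3 with bilirubin > 1.5 × ULN) through their day-7 samples, 8/1.6 and 5/1.6. The loss is in the rows at 2 × ULN.
- B is the patient on whom the conflicting window sentences give opposite answers.

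**A sequential rule on the same patients.** Suppose liver tests to day 30 are used, and a case counts when bilirubin crosses 2 × ULN on the day of, or within 30 days after, an ALT/AST value > 3 × ULN. A and B qualify in a single sample. In C, bilirubin crosses 14 − 7 = 7 days after the last ALT value above 3 × ULN. In D, it crosses 6 − 0 = 6 days after. All four are counted.

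**What one case is worth**
- Planned patients per dose under 3:3:1: 3/7 × 1,570 = 673.
- One case: 1/673 = 0.15%.
- Zero cases, one-sided 95% upper bound: 1 − 0.05^(1/673) = 0.44%.
- SAP 2.5.1 says the study was terminated early, so actual arms may be smaller. If an arm held 400 patients (assumed), the bound would be 1 − 0.05^(1/400) = 0.75%.

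These figures show how much one patient matters. They do not measure how often a patient is missed.

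**The case against.** The strongest defence is that the same-sample rule is an open choice, paired on purpose with a plot that drops it, and that Hy's law is settled by case review and not by a table row. Much of this stands. It disposes of several stronger readings that a reader might infer:

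- **That such a patient is reported as no case.** The documents do not support this. The patient enters the single-parameter rows (for example ALT > 8 × ULN) and the listings of notable liver values and liver events. SAP 2.8.6 lists all liver event overview data with no window. Under Protocol Appendix 3 and Section 7.5 the event is also a potential idiosyncratic reaction and goes to the DMC. A serious event stays treatment emergent for 30 days.
- **That values after day 7 are definitely excluded, and from eDISH too.** This is inference. The limit comes from SAP 2.8.3 and the general part of 2.8.3.3; the liver paragraph is worded without it, and the plot has no stated cut-off. If the plot uses all post-baseline data, it shows all four patients above.
- **That every bilirubin rise after stopping is lost.** Patient A shows otherwise. By Table 14-2, ALT/AST above 5 and up to 8 × ULN leads to a stop only if it persists beyond 2 weeks, so early rises there can be on treatment.
- **That every combined row is affected.** The ALT/AST-with-symptoms row has one laboratory parameter and takes its symptoms from the liver events eCRF, so the same-sample rule does not govern it.
- **That the stopping rule systematically pushes the bilirubin peak out of the window.** The documents say nothing about the lag between the two peaks.

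The defence does not show that listings or a plot replace a tabulated count by arm. Nor does it remove the conflict over the window. A plot and table may properly differ by design, but they should not differ because their data cut-offs were left open.

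**Conclusion.** The point holds as an undercount confined to the combined laboratory rows of Table 2-4. The row can omit a patient whose parameters cross at different times. On the natural reading it also omits one who crosses more than 7 days after the last dose. The protocol's potential Hy's law definition has neither condition, so the tabulated count can be narrower than the case definition used at the sites.

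The 7-day part rests on applying SAP 2.8.3 and the general notable-values text to the liver paragraph. The same-sample part does not depend on that reading. The frequency of affected patients cannot be estimated from the documents. The consequence is one or a few patients in a row expected to hold few, where one case is 0.15% of a planned arm. The primary time-to-event analyses are not affected. The contradiction over the window needs resolving in any event.

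**What to change.** In SAP 2.8.3.3:

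1. **State one data window for both Table 2-4 and eDISH, and make it include liver tests after discontinuation.** It could be at least 30 days after the last dose, which the SAP already uses for serious AEs, or all post-baseline data, as the liver paragraph literally says. The second is wider: Table 14-2 allows follow-up of a persistent elevation for up to 6 months. Align 2.8.3 and 2.8.3.3 with the choice.
2. **Say that local results count.** Protocol 7.3 allows repeat liver tests at a local laboratory, with results recorded on the liver CRF pages when a liver event follows. A program reading only central laboratory data could miss them.
3. **Add a supplementary column for the ALT/AST with bilirubin criteria, including Hy's law.** Count the criterion as met when bilirubin crosses its threshold on the day of, or within a pre-stated interval after, the ALT/AST elevation, with ALP assessed at that elevation. Thirty days would serve; it is an analysis convention, not a figure from the documents for this purpose.
4. **Keep the same-sample, 7-day count alongside,** so that the existing result is preserved. The ALP with bilirubin rows gain from the wider window only.

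The cost is SAP wording and programming, including merging local results from the liver CRF. No new tests are needed, because the protocol already requires the follow-up. A few cases not due to drug may enter and need narrative review.
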